#### Secondary Endpoints:

We hypothesize that, compared to smokers who receive the Control intervention, smokers who receive the Intervention will:

- a) have more quit attempts during the 7-month study period (Aim 2 Hypothesis 2.1)
- b) have higher motivation to quit at 1-month post-appointment and 3- and 6-months follow-up (Aim 2 Hypothesis 2.2)
- c) have greater biochemically verified abstinence rates at 1-month post-appointment and 3 and 6 months follow-up (Aim 3 Hypothesis 3.1)

Alternatively, our null hypotheses are that there will be no difference between the two study groups on these secondary endpoints.

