Aim 2. Quit attempts and motivation to quit, and Aim 3. Biochemically verified abstinence. Dichotomous data on quit attempts, motivation to quit, and biochemically verified abstinence will be collected at one-month post-appointment (the end of the text message program), and at 3 and 6 months follow-up. Data on quit attempts will be based on the question "Since last contact, how many times have you stopped smoking for at least 24 hours because you were trying to quit smoking (not due to illness/hospitalization)?" Our main analyses for this outcome will examine the dichotomized outcome of 'any quit attempt', although we will collect data on the number of attempts and duration. Motivation to quit will be based on the question "Are you seriously thinking of quitting smoking in the next 30 days (yes or no)?" To determine point-prevalence abstinence, participants will be asked "In the last 7 days, have you smoked any cigarettes at all, even a puff?" For those responding 'no', biochemical verification will be implemented with salivary cotinine, with abstinence defined as cotinine values < 15 ng/mL. If participants indicate use of Nicotine Replacement Therapy or electronic nicotine delivery system use, these data will be recorded and reported separately from cotinine-validated abstinence. For these outcomes, the Intervention will be compared to the Control on data from 1-month post-appointment and at 3 and 6 month follow-up through mixed effect logistic regression models with random intercepts for longitudinal dichotomous data. These models will include indicator variables for intervention group, time, and interaction between intervention group and time (which will model and test whether changes in motivation to quit follows different patterns over time in the

Based on the NIH Behavioral and Social Intervention Clinical Trial Protocol Template v3.0 - 20180827

Intervention vs. Control group). Intervention effects will be described through odds ratios and 95% confidence intervals. In the case of significant intervention by time interaction, separate odds ratios will be given for intervention effects at each time point. We will control for age, gender, race/ethnicity, and variables identified through preliminary analyses as significantly differing between study groups.

---

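### Section 9.4.3 gives visit-specific odds ratios only after a significant interaction test and leaves the other branch undefined, although Hypotheses 2.2 and 3.1 are stated at 1, 3 and 6 months

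*Combined protocol and SAP*

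**What the plan says.** Section 9.1 (Secondary Endpoints) states two hypotheses by visit. Hypothesis 2.2 is that Intervention participants will "have higher motivation to quit at 1-month post-appointment and 3- and 6-months follow-up". Hypothesis 3.1 is that they will "have greater biochemically verified abstinence rates at 1-month post-appointment and 3 and 6 months follow-up". The table in section 3 also places verified abstinence at the three follow-ups. Hypothesis 2.1 (quit attempts) is stated over the whole 7 months, not by visit.

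Section 9.4.3 analyses these outcomes with "mixed effect logistic regression models with random intercepts for longitudinal dichotomous data". The terms are group, time and group by time, and the outcome data are those from the three follow-ups. On reporting it says "Intervention effects will be described through odds ratios and 95% confidence intervals" and then "In the case of significant intervention by time interaction, separate odds ratios will be given for intervention effects at each time point". It does not say which odds ratio is given when the interaction is not significant, or whether the interaction term then stays in the model. No other section promises visit-specific odds ratios for these outcomes or names a key visit for them.

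**The concern.** Two hypotheses are framed at each visit, but whether an estimate appears at each visit depends on a preliminary test at the 0.05 level. That test asks only whether the group effect differs among the three follow-ups, and the protocol states no power for it.

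Change over time is plausible here on the protocol's own account. Section 2.1 criticises earlier studies because their effects wore off. Section 4.3 justifies the later follow-ups as a check on whether EBT engagement lasts. The near-daily messages stop at four weeks, with only occasional reminders afterwards (section 6.1.1). If the effect on abstinence fades and the test misses it, readers may see one average odds ratio that suggests a benefit at 6 months where there is none. If the effect appears late, the average understates it.

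**Working it through.** **Inputs from the documents.** 364 analysable participants, so 182 per arm; two-sided 0.05; no multiplicity adjustment (section 9.2). Three follow-ups, so the interaction has 2 degrees of freedom (section 9.4.3). Quit rates are expected to be low, without a figure (section 2.1). 40-80% of smokers are not ready to quit within 30 days (section 3), so 20-60% are.

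**Assumptions.** Control rates of 5% and 10% for abstinence, 20% and 40% for motivation; no missing visits; no covariates.

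**1. The plan's own figure.** The only power given for a binary outcome is for any EBT use, 22.7% v 37.6%. With mean rate 0.3015, √(2×0.3015×0.6985) = 0.649 and √(0.227×0.773 + 0.376×0.624) = 0.640:
- n per arm = [(1.96×0.649 + 0.842×0.640)/0.149]² ≈ 148, or 296 in total (stated 300).
- With 182 per arm, z = (0.149×√182 − 1.96×0.649)/0.640 = 1.15, so power is 0.875 (stated 0.87).

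The stated figures reproduce. They say nothing about the interaction test.

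**2. How often the condition is met.** Two methods were used at 182 per arm:
- *Marginal:* three correlated binary visits (latent correlation 0.5), Wald interaction test.
- *Random intercept:* the section 9.4.3 model without covariates, intercept SD 1.5 or 2.5, likelihood-ratio test, 250 replicates (simulation error up to about 3 points).

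| Pattern at 1/3/6 months | Control rate | Method | Interaction significant | Common OR | True 6-month OR |
|---|---|---|---|---|---|
| Intervention 5/5/12% | 5% | marginal | 39-43% | about 1.5 | 2.6 |
| Intervention 12/8/5% | 5% | marginal | 26-36% | about 1.7 | 1.0 |
| OR 2.05/1.5/1.0 | 5% | random intercept | 21-23% | 1.60-1.81 | 1.0 |
| same | 10% | random intercept | 40-42% | 1.64-1.94 | 1.0 |
| same | 20% | random intercept | 54-64% | 1.69-2.02 | 1.0 |
| same | 40% | random intercept | 67-85% | 1.72-2.09 | 1.0 |
| OR 2.05 throughout | 5-40% | random intercept | 4-8% | estimates the effect at every visit | 2.05 |

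Ranges in the marginal rows are across repeated sets of runs. The second varies by more than the simulation error at 400 replicates (√(0.3×0.7/400) = 2.3 points), so it is best read as about a third. In every run it is a minority.

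Other fades give other figures. OR 2.05/2.05/1.0 is flagged in 23-27% of trials at 5% and 43-52% at 10%. OR 3.0/1.7/1.0 is flagged in 39-49% and 68-82%.

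**3. Hand check of the common odds ratio.** Weight each visit's log odds ratio by 1/variance, where variance = 1/(182·p_C·(1−p_C)) + 1/(182·p_I·(1−p_I)).
- 12% v 5%: OR = (0.12/0.88)/(0.05/0.95) = 2.59, log 0.952, weight 5.96.
- 8% v 5%: OR 1.65, log 0.502, weight 5.25.
- 5% v 5%: OR 1.0, log 0, weight 4.32.
- Late effect: 0.952×5.96/(4.32+4.32+5.96) = 0.389, OR 1.5.
- Fade: (0.952×5.96 + 0.502×5.25)/(5.96+5.25+4.32) = 0.535, OR 1.7.

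Both agree with the simulation. Restricting to trials with a non-significant interaction, the only ones where a common odds ratio would stand alone, also gave medians of about 1.5 and 1.7. The random-intercept medians are over all trials and on the subject-specific scale. A null 6-month effect is 1.0 on either scale, so the scale does not explain the gap.

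**4. If the term is kept instead.** With indicator coding and the interaction retained, the group coefficient is the odds ratio at the reference visit only. The text does not rule this reading out.

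**The case against.** The strongest reply is that the rule does little harm in many realistic cases, and much of it stands.

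- A reader might infer that the visit-specific hypotheses will usually go unanswered. The documents do not support that. Under a constant effect the condition fails about 95% of the time, but one odds ratio then estimates the effect at every visit fairly.
- A reader might infer that the interaction test is weak in general. At 20-40%, plausible for motivation given the readiness figures in section 3, the same fade is flagged in 54-85% of trials.
- A reader might infer that a common odds ratio is wrong at every visit. In the 12/8/5% pattern the pooled 1.7 is close to the 3-month value of 1.65; the error is at 1 and 6 months.
- A reader might infer that the plan commits to a single pooled odds ratio. It does not; section 9.4.3 leaves that branch undefined.
- A reader might infer that Hypothesis 3.1 should be judged at 6 months alone, because sections 9.3 and 9.4.2 base primary analyses on participants evaluated then. That text defines who is analysed, not a key visit for abstinence. The switch would also cost power: for a constant odds ratio of 2.05, about 0.40 against 0.72 for a common odds ratio at a 5% control rate, and 0.63 against 0.90 at 10%.

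These are also secondary outcomes, and section 9.4.1 promises a formal SAP before unblinding, where the gap could be closed. None of this justifies making the estimates depend on the test.

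**Conclusion.** The concern holds in a limited form. The conditional rule does not match Hypotheses 2.2 and 3.1, and the non-significant branch is undefined. The practical risk lies with verified abstinence. For a fade from an odds ratio of about 2-2.6 to 1.0, or an effect confined to 6 months, separate odds ratios would appear in about 21-43% of trials. A common odds ratio in the rest would be about 1.5 for the late effect and 1.6-1.9 for the fade, reaching 2.1 at higher control rates.

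This rests on assumed control abstinence of 5-10%, 182 per arm, complete visits, the patterns listed and, for the misstatement, a common odds ratio being what is reported. Steeper fades at 10% are mostly flagged. The problem is smaller for motivation, absent under a constant effect, and does not concern Hypothesis 2.1.

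**What to change.** Delete the condition in section 9.4.3. For motivation and abstinence, state that the odds ratio and 95% interval at each of the three follow-ups will be reported from the interaction model already specified, whatever the interaction p-value. Beside them, prespecify one overall odds ratio, with its definition (interaction term dropped, or a stated average over visits), to carry the hypothesis test. Describe the interaction test as descriptive.

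This needs no new data, model or sample size, and can go into the formal SAP. The costs are more estimates in the table and visit-specific intervals without multiplicity adjustment. With no effect at any visit, the chance that at least one of three intervals excludes 1 is about 14% (1 − 0.95³ = 0.143 if independent; 13.8-14.2% simulated). They should therefore be labelled as estimates, not as three separate tests.

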#### 9.4.4 SAFETY ANALYSES

N/A

---

#### 9.4.5 BASELINE DESCRIPTIVE STATISTICS

Baseline demographic and smoking-related characteristics will be compared for those randomized to the Intervention vs. Control groups. Because of randomization, we do not anticipate baseline differences between groups, but if significant differences are found, those variables will be considered as potential confounders in later analyses. Categorical characteristics will be described through percentages and compared across groups through chi-square tests, and continuous measures will be described through means and standard deviations and be compared through t-tests.

---

#### 9.4.6 PLANNED INTERIM ANALYSES

N/A

---

#### 9.4.7 SUB-GROUP ANALYSES

Differences in the effect of the Intervention vs. Control on any EBT utilization over the 7-month study period will be examined through logistic regression models including interaction terms between the intervention and demographic and baseline characteristics. We will examine perceived stress, readiness to quit smoking at baseline, gender, and race/ethnicity as possible effect modifiers.

---

#### 9.4.8 TABULATION OF INDIVIDUAL PARTICIPANT DATA

Individual participant data will not be presented.

---

#### 9.4.9 EXPLORATORY ANALYSES

Aim 4. Mediation. Exploratory analyses will examine the role of social cognitive factors as mediators of the intervention effect on any EBT utilization. Our analyses will account for the temporal precedence assumption of mediation. If participants utilize the EBT within one month of their dental appointment, we will compute change from baseline to the time point prior to first initiation of any EBT. If participants contact an EBT after the first month, we will compute change scores between baseline and end of treatment (1-month post-appointment). Our primary approach to establishing mediation effects will be the product of coefficients method, which utilizes a multiple mediation model to simultaneously test the effects of the potential mediators. Corresponding standard errors will be calculated using bootstrapping (10,000 bootstrapped sample). Multiple mediation allows for simultaneous testing of the

Based on the NIH Behavioral and Social Intervention Clinical Trial Protocol Template v3.0 - 20180827

effect of a set of mediators while controlling for the effects of the others, and a comparison of the effects of the mediators to determine the relative influence of each mediator.

Aim 4. Effect modification. We will explore whether the Intervention has different effects on any EBT utilization over the 7-month study period for different subpopulations by examining interactions between potential moderators and intervention using logistic regression models. We will examine perceived stress, readiness to quit smoking at baseline, gender, and race/ethnicity as potential effect modifiers.

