## 1 PROTOCOL SUMMARY

### 1.1 SYNOPSIS

Title:	A Smoking Cessation Induction Intervention Via Virtual Reality Headset During a Dental Cleaning: Randomized Controlled Trial
Grant Number:	1UG3DE028866
Study Description:	
The primary aim of the UH3 Stage III randomized efficacy trial is to test whether a video-based smoking cessation induction intervention delivered via virtual reality (VR) headset during part of a dental hygiene appointment increases dental patients' utilization of evidence-based treatments (EBTs) for smoking cessation (Massachusetts State quitline, clinic-based programs, NCI text message program [SmokefreeTXT], nicotine replacement products or other smoking cessation medications) within 7-months post-dental hygiene appointment. 437 cigarette smokers scheduled for dental prophylaxis or scaling and root planing at the Boston University Goldman School of Dental Medicine (BUGSDM) patient treatment center or Tufts University (TU) School of Dental Medicine Comprehensive Care Clinic or Periodontal Clinic will be randomized (1:1) to either the Intervention (smoking cessation video via VR headset, brochure about EBTs, and four-week of interactive, automated and tailored text message program to motivate EBT utilization) or Control group (control video on relaxation via VR headset, brochure about EBTs, and assessment-only text messages). The primary hypotheses are: Hypothesis 1.1: Participants in the Intervention will be more likely to contact and engage with EBTs and Hypothesis 1.2: Participants in the Intervention will have greater EBT utilization. The secondary hypotheses are: Hypothesis 2: Participants in the Intervention will have greater quit attempts and motivation to quit. Hypothesis 3: Participants in the Intervention will achieve higher biochemically confirmed smoking cessation rates at follow-up. Hypothesis 4: The Intervention will directly affect the putative mediators of intervention effect, which will in turn affect EBT utilization. The role of moderators will be exploratory.

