### 3 OBJECTIVES AND ENDPOINTS

OBJECTIVES	ENDPOINTS	JUSTIFICATION FOR ENDPOINTS	PUTATIVE MECHANISMS OF ACTION
Primary			
To test the efficacy of the Intervention vs. Controls in increasing contact with, and utilization of, EBTs over a 7-month study period.	
 
-Any EBT contact over the 7-month study period.
 
-Total number of EBTs contacted – ranging 0 to 4 – over the 7-month study period
 
-EBT utilization index score over the 7-month study period
 
	Because effective cessation programs already exist, innovations are needed to drive smokers to engage with them. 40-80% of smokers are not ready to quit within 30 days, and efforts are needed to reach smokers with motivational interventions in their natural settings. Because we are proactively reaching patients, they may or may not be ready to quit smoking. Therefore, quit rates would be expected to be low if we were focusing on cessation, necessitating a very large sample to be able to compute power. The goal of the study is to test whether a clinic-based intervention that reduces provider burden and has minimal patient burden can drive patients to make contact with EBTs. Our prior research has shown that smokers who are not motivated to quit either lack knowledge about the EBTs, do not know how to access EBTs, and/or have myths about EBTs. The video-based intervention and subsequent 4-week text message program addresses these barriers, and provides motivational strategies to make contact with EBTs.	The VR video intervention including the subsequent 4-week text message program target social cognitive theory constructs (e.g., motivation, self-efficacy, outcome expectations) which are the hypothesized mechanisms that mediate the effect of the intervention on the primary study endpoints.
Secondary			
To test the efficacy of the Intervention vs. Controls in motivating smokers to use a combination of medication and counseling.	-Combination of at least one form of counseling EBTs (state quitline counseling, clinic-based counseling, text messaging) and at least one form of medication (nicotine replacement	Participants may utilize more than one EBT and will be encouraged to do so. Evidence shows that a combination of counseling and medication is more effective than either treatment alone.	

OBJECTIVES	ENDPOINTS	JUSTIFICATION FOR ENDPOINTS	PUTATIVE MECHANISMS OF ACTION
	therapy or tablet medication) over the 7-month study period.		

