## 4 STUDY DESIGN

### 4.1 OVERALL DESIGN

This study is a 2-arm, stage III randomized controlled efficacy trial. Three hundred seventy-six patients will be recruited at Boston University GSDM patient treatment center or TU comprehensive care (or Periodontal) clinic, and randomized to the Intervention group or the Control group. To account for participants who become ineligible post-informed consent (e.g., do not complete baseline activities, do not show up to dental visit) and thus are not randomized, we estimate that approximately 700 subjects will be enrolled. Our aim is to test whether the Intervention administered to dental patients during teeth cleaning increases contact with, and utilization of, EBTs. Smokers randomized to the Intervention group will receive: 1) the smoking cessation video intervention via VR headset during their teeth cleaning, 2) brochure about EBTs, and 3) 4-weeks of tailored, interactive, and automated text messages to motivate engagement with EBTs plus periodic text message reminders throughout the study. The Control group will watch a relaxation video through the VR headset during their teeth cleaning, receive a brochure about EBTs, and receive assessment-only text messages. We chose a 'relaxation video' because this topic is at least somewhat connected to the teeth cleaning experience (e.g., to ease dental anxiety and discomfort), rather than watching a video on general health and wellness, for example.

The Primary Objective is to test the efficacy of the Intervention vs. Controls in increasing contact with, and utilization of, EBTs over a 7-month period. Hypothesis 1.1 states: Participants randomized to the Intervention will be more likely to engage (make contact with) EBTs. Hypothesis 1.2 states: Participants randomized to the Intervention will have greater EBT utilization (e.g., more quitline counseling sessions, more days in the text message program).

The Secondary Objectives are: 1) To test the effect of the Intervention vs. Controls on quit attempts and on motivation to quit. Hypothesis 2 states: Participants in the Intervention will make more quit

Based on the NIH Behavioral and Social Intervention Clinical Trial Protocol Template v3.0 - 20180827

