attempts and increase their motivation to quit; 2) To test the efficacy of the Intervention vs. Controls on biochemically verified smoking abstinence. Hypothesis 3 states: Participants in the Intervention will achieve higher rates of point-prevalence abstinence at follow-up; 3) To assess the mechanisms through which intervention effects occur (mediators such as self-efficacy, motivation, and outcome expectations) and to identify subpopulations for whom intervention effects differ (moderators such as gender and motivation to quit). Hypothesis 4 states: The Intervention will directly affect the putative mediators of intervention effect, which will in turn affect EBT engagement (contact) and utilization. The role of moderators will be exploratory.

Participants will be randomized (1:1) at the dental clinic, after receiving the study brochure and before watching the videos during their teeth cleaning. Randomization will be implemented by employing a stratified block procedure with small, random size blocks and will be stratified by motivation to quit (ready to quit smoking in 30 days vs. not ready to quit within 30 days). To avoid randomization errors, randomization will be configured within REDCap, the secure web application used to build and manage the questionnaires and study forms which is programmed and managed by the BU Biostatistics and Epidemiology Data Analytics Center (BEDAC). A biostatistician will build the randomization program. The study RA will trigger randomization by pressing the feature on the REDCap eCRF form using an iPad. All dental providers will be masked to treatment condition because both the Intervention group and the Control group will be watching a video through the VR headset. Only the PI, project director, statistician, and study RA who is in the clinic will be unmasked to treatment condition.

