- EBTs for smoking cessation will be operationalized as: 1) utilization of any EBT over the 7-month study period; 2) total number of EBTs utilization during the 7-month study period (ranging 0 to 4); 3) EBT utilization index score (UIS; obtained by first computing a proportion of utilization score for each of the EBTs for each participant, and then adding up the individual proportion scores; see section 9.4.1 for details); 4) combination of at least one form of non-pharmacologic EBT and at least one form of pharmacologic EBT over the 7-month study period.
- Quit smoking attempts (assessed at Time 4 – 6). The number of quitting smoking attempts participants have made, since last contact, that have lasted 24 hours or more and that were not due to hospitalization or illness.
- Motivation to quit smoking (assessed at Time 4 – 6). Participants' motivation to quit smoking within 30 days (yes vs no).
- Smoking abstinence (assessed at Time 4 – 6). Seven-day point-prevalence abstinence (7-day ppa) assessed by self-report of no smoking, not even a puff, in the past 7 days and salivary cotinine level < 15 ng/mL.
- Mediators of treatment effects (assessed at Time 2 – 6). Theoretically driven constructs hypothesized to mediate any observed intervention effect (EBT utilization, quit smoking attempts, motivation to quit, or smoking abstinence) include the social cognitive theory constructs of motivation, self-efficacy, and outcome expectancies.
- Moderators or treatment effects (assessed at baseline). Moderating factors include sex, race or ethnicity, perceived stress and readiness to quit smoking.

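### Hypothesis 4 covers EBT contact and EBT utilization, but the only planned mediation model has the binary any-EBT outcome, so no exploratory model relates a mediator to amount of use

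*Combined protocol and SAP*

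**What the plan says.** Section 4.1 gives the hypothesis: "Hypothesis 4 states: The Intervention will directly affect the putative mediators of intervention effect, which will in turn affect EBT engagement (contact) and utilization". The same section separates the two terms. Hypothesis 1.1 concerns contact: "Participants randomized to the Intervention will be more likely to engage (make contact with) EBTs". Hypothesis 1.2 concerns amount: "Participants randomized to the Intervention will have greater EBT utilization (e.g., more quitline counseling sessions, more days in the text message program". The synopsis (Section 1.1) names utilization only: "The Intervention will directly affect the putative mediators of intervention effect, which will in turn affect EBT utilization".

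Section 3 describes the social cognitive constructs as the "hypothesized mechanisms that mediate the effect of the intervention on the primary study endpoints". The primary endpoints in that table are any EBT contact, the number of EBTs contacted (0 to 4) and the UIS. Section 8.1 is wider still. The effects it lists as possibly mediated are "EBT utilization, quit smoking attempts, motivation to quit, or smoking abstinence".

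The analysis plan is narrower than all of these. Section 9.4.9 reads: "Exploratory analyses will examine the role of social cognitive factors as mediators of the intervention effect on any EBT utilization". Section 9.4.2 treats any EBT utilization as binary and analyses it by logistic regression. Section 9.1 restricts Aim 4 to engagement with any EBT. The UIS (Section 9.4.2), the number of EBTs and the counseling-plus-medication indicator (both Section 9.4.3) get models of the arm effect only, with no mediator in them.

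**The concern.** The hypothesis has two outcomes and the plan models one. A mediator could leave the decision to start a treatment unchanged and still make those who start stay longer. The planned model would report such a mediator as not mediating, although it does part of what Section 4.1 predicts.

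The protocol's own theory makes this path plausible. Section 2.1 says self-efficacy governs how long a person persists, as well as which activities they choose. Section 2.2 links length of counseling and medication use to abstinence. Section 2.1 also lists testing mechanisms of change among the gaps the trial is meant to fill. What is at stake is the trial's account of how the intervention works. Whether it works is not affected.

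**Working it through.** **Step 1: compare the sections.**

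| Section | Outcome said to be mediated |
|---|---|
| 1.1 | EBT utilization |
| 3 | The primary endpoints: any contact, number of EBTs, UIS |
| 4.1 | Contact and utilization |
| 8.1 | EBT utilization, quit attempts, motivation to quit, abstinence |
| 9.1, Aim 4 | Engagement with any EBT |
| 9.4.9 | Any EBT utilization (binary) |

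Sections 9.1 and 9.4.9 agree with each other. Sections 3, 4.1 and 8.1 are each wider. There is no mediation model for a quantity-of-use outcome anywhere in the plan. The plan gives no power figure for mediation, so there is none to reproduce.

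**Step 2: how much the any-EBT model could miss (assumed scenario).**

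From Section 9.2: 455 less 20% = 455 × 0.80 = 364 analysed, or 182 per arm; any EBT use 22.7% in Control and 37.6% in Intervention.

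Assumed, because the documents give no values: one mediator; arm effect on it 0.4 SD; dose among users = 0.6 + g × mediator + normal error with SD 0.3, clipped to 0.05–1.5; UIS = use × dose; robust errors for UIS. Mediation is declared when both the arm-to-mediator and mediator-to-outcome paths have p < 0.05. There were 4,000 simulated trials per setting.

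| Setting | Any-EBT model | UIS model |
|---|---|---|
| g = 0, no effect on starting | 0.050 | 0.050 |
| g = 0.10, dose only | 0.049 | 0.358 |
| g = 0.15, dose only | 0.049 | 0.653 |
| g = 0.20, dose only | 0.055 | 0.838 |
| Starting only (log OR 0.3 per SD) | 0.686 | 0.582 |

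Hand check of the 5%: the arm-to-mediator path has z = 0.4 × √(182/2) = 3.82, so power is Φ(3.82 − 1.96) ≈ 0.97. With no true mediator-to-starting effect, joint significance is about 0.97 × 0.05 ≈ 0.048.

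**Step 3: sensitivity.** With three mediators in the model, as planned (assumed correlation 0.5), UIS detection at g = 0.10, 0.15 and 0.20 falls to about 0.25, 0.48 and 0.67. With one mediator and an arm effect of 0.2 SD, g = 0.10 and 0.15 give about 0.17 and 0.34. That is in line with the weaker first path: z = 0.2 × √91 = 1.91, power Φ(1.91 − 1.96) ≈ 0.48.

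**Step 4: what a UIS model measures.** UIS is zero for non-users, who are 100 − 22.7 = 77.3% of Control and 100 − 37.6 = 62.4% of Intervention at the planning rates. The last row of the table shows the consequence: a mediator that acts only on starting still gives a positive UIS result 58% of the time. Users would number about 0.227 × 182 + 0.376 × 182 = 41.3 + 68.4 ≈ 110.

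**The case against.** The best defence is that Section 9.1 is the formal statement of the hypotheses, that its Aim 4 matches Section 9.4.9, and that Sections 3 and 4.1 are merely loose. The vocabulary is indeed mixed: the null for Hypothesis 1.1 in Section 9.1 pairs contact with utilization for what is a yes/no outcome. This shows that narrowing the text would also restore consistency. It does not remove the mismatch, because Hypothesis 1.2 is about amount in both Section 4.1 and Section 9.1, and Section 3 names the primary endpoints without exception.

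The magnitude is also open to challenge. The 5% follows by construction once the mediator is set not to affect starting, and the UIS figures depend on inputs found nowhere in the documents. Both points stand. The simulation shows what kind of mediator would be missed; it does not show that such a mediator is likely. It also uses joint significance, where the plan uses the product of coefficients with bootstrapped errors.

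Four stronger readings are tempting and should not be drawn:

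- A reader might infer that the utilization part will never be tested. Section 9.4.1 promises a formal SAP before unblinding, so the supported statement is that it is not planned in this document.
- A reader might take a UIS mediation model as the test of the dose part. It is not, because it mixes starting with dose (Step 4).
- A reader might conclude from Section 8.1 that motivation is set to mediate itself. The outcome is a yes/no item about quitting within 30 days; the mediator is described as a social cognitive construct, also assessed weekly by text. The documents do not show that both use the same item.
- A reader might think quit attempts and abstinence should be struck from Section 8.1, or that its list lets the outcome be chosen after the results. Section 8.1 describes measures, and Section 9.4.9 fixes one outcome. Nothing in the documents makes those outcomes unsuitable for mediation.

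**Conclusion.** The mismatch is established from the text alone. Sections 3 and 4.1 extend mediation to amount of use, and Sections 9.1 and 9.4.9 do not model it. A mediator acting purely on dose would be found by the planned model at about the 5% chance rate. Under the assumed inputs a UIS model would find it about 36% to 84% of the time, and less often with three correlated mediators or a smaller arm effect on the mediator. At the smallest slope the added model would usually miss a true effect, so it improves coverage of the hypothesis without guaranteeing an answer.

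The weight is modest. The mediator work is exploratory, the arm effect on UIS is already analysed as a primary outcome, and no primary conclusion depends on this point.

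**What to change.** 1. In Section 9.4.9, add a second exploratory multiple-mediator model with UIS as outcome and the same mediators and covariates. Describe it as mediation of total utilization, which combines starting and dose.
2. To speak to dose itself, add a descriptive model of UIS among EBT users only. State that this subset is selected after randomization, and that mediator change measured before first EBT use does not capture change after starting. At the planning rates it would rest on about 110 people.
3. State the mediator-change window for participants who never use an EBT. The timing rule in Section 9.4.9 covers early and later users only, and both the existing model and the UIS model need it.
4. Align the mediated outcomes named in Sections 3, 4.1, 8.1 and 9.1 with those that Section 9.4.9 analyses. For the other outcomes listed in Section 8.1, either plan a model or say that none is planned.

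The cost is one or two more exploratory models on data already being collected, plus wording edits that can be made before the formal SAP is finalised. The downside is a longer list of exploratory results. Restricting Hypothesis 4 to any EBT use throughout would cost less, but would give up the persistence mechanism that the theory section puts forward.
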